1.2 Revision Control

Protocol Version	Updated SAP version number	Section number changed	Description of change	Date changed
3.0	1.0			
3.0	1.1*	6.2	Clarification that the analyses for the primary outcome will be adjusted for sex as for all secondary analyses	February 22 nd , 2024
		6.2.3	Clarification that the median difference with 95% CI will be performed using quantile regression models	
		Table 1	Modification of the legend to reflect these clarifications	

[figure not shown]
*These points required clarification and do not represent a change in the analysis plan. The clarifications were made before the randomization code was opened.

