3.1 Trial Design

HEMOTION is a pragmatic, parallel group, multi-centre, open label blinded-endpoint, randomized trial⁴. Once reaching a Hb ≤ 100 g/L and after a site investigator has confirmed eligibility, participants will be randomly allocated to either a liberal (experimental) or a restrictive (control) RBC transfusion strategy. The trial intervention is initiated within 3 hours in patients meeting the threshold for transfusion in their respective group. All primary and secondary outcomes are assessed centrally by trained research personnel blinded to the intervention to minimize the risk of bias during data collection. Tertiary outcomes are assessed at participating sites, unblinded to the intervention but using standardized definitions.

The control strategy: Patients in the restrictive transfusion strategy group receive an RBC transfusion only if their Hb is ≤ 70 g/L.

The experimental strategy: Patients in the liberal transfusion strategy group receive an RBC transfusion if their Hb is ≤ 100 g/L. This threshold, shown to be effective in maintaining adequate cerebral oxygenation, is considered acceptable by clinicians caring for critically ill patients with neurological injuries.

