6.1.3 Tertiary outcomes

- The number of red blood cell units transfused in the ICU.
- The lowest daily Hb level recorded in the ICU.
- Infections categorized as any infection, pneumonia, bacteremia, sepsis/septic shock, central nervous system infection. Both the proportion of patients who had an infection and the proportion of patients who had each category of infection.
- The length of time spent on mechanical ventilation in the ICU.
- The length of stay in the ICU.
- The length of stay in the hospital.
- Complications of red blood cell blood transfusions.

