6.2.3 Tertiary outcomes analyses

Main analyses:

The analyses of the tertiary outcomes are descriptive and exploratory. We anticipate that many of these outcomes will occur infrequently, limiting our ability to conduct comprehensive multivariate analyses. Therefore, all analyses will be unadjusted and no sensitivity analyses will be conducted.

- The number of red blood cell units transfused per patient in the ICU will be analyzed using Student's t-test. We will report means, standard deviations, between-group difference and 95% CI. If data is not normally distributed, we will use the Wilcoxon rank sum test and report medians with interquartile ranges as well as median difference with 95% CI.
- The mean lowest daily Hb will be graphically displayed with associated 95% CI at each time point.
- The proportion of patients who had infections or transfusion complications will be analyzed using a Chi-square test. We will report an unadjusted RR.
- Duration of mechanical ventilation, as well as the length of stay in the ICU and the hospital, will be analyzed using the Wilcoxon rank sum test and reported with medians and interquartile ranges as well as median difference with 95% CI using quantile regression models.

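### For RBC units per patient, the non-normal fallback in SAP 6.2.3 is a median difference with 95% CI, which suits tied whole-number counts poorly; the mean difference should be kept whatever the distribution (minor)

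*SAP*

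**What the plan says.** Section 6.1.3 defines the outcome as a count: "The number of red blood cell units transfused in the ICU". Section 2.2 lists it among the tertiary objectives.

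In section 6.2.3 the first-line analysis is Student's t-test with means, standard deviations, the between-group difference and a 95% CI. If the data are not normally distributed, "we will use the Wilcoxon rank sum test and report medians with interquartile ranges as well as median difference with 95% CI". No interval method is named there. Within 6.2.3, quantile regression appears only in the bullet on ventilation time and lengths of stay: "as well as median difference with 95% CI using quantile regression models". The version 1.1 row in section 1.2 is not limited to those durations: "Clarification that the median difference with 95% CI will be performed using quantile regression models".

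Overview Table 1 lists only the t-test for this outcome. The Table 3 shell in Appendix 2 shows mean ± SD with a between-group difference. Section 6.2 promises a 95% CI for every treatment effect and difference. Section 6.2.3 also sets the status of this family: "The analyses of the tertiary outcomes are descriptive and exploratory".

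**The concern.** The effect measure for blood use depends on a normality condition that this outcome will almost surely fail. Two things are then lost.

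- **The interval.** The usual quantile-regression standard error needs a continuous, positive density at the median. Whole-number counts with heavy ties have none, so the nominal 95% level is not controlled.
- **The quantity.** Extra blood per patient is a mean: multiplied by the number of patients, it gives the total units used. A median difference of counts takes few values and does not convert to a total.

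At stake is how accurately the difference in blood use between the strategies is reported. Whether a difference is found is not in question.

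**Working it through.** **1. The plan's own figures.** The SAP gives no zero fraction, mean or SD for RBC units, so there is nothing to reproduce for this outcome. The trial size used as input does reproduce (section 3.5): 712 / (1 − 0.02)² = 712 / 0.9604 = 741.4, rounded up to 742. At 1:1 that is 371 per arm. After 2% dropout it is 742 × 0.98 / 2 = 363.6, or about 364 per arm.

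**2. Shape of the outcome.** Randomization follows "Once reaching a Hb ≤ 100 g/L and after a site investigator has confirmed eligibility", and section 3.1 sets the liberal trigger at the same level. An adherent liberal patient therefore receives at least 1 unit. Restrictive patients "receive an RBC transfusion only if their Hb is ≤ 70 g/L", so many probably receive none. The result is bounded, skewed whole numbers with a spike at zero in one arm. This is inferred from the design; the SAP does not state it.

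**3. Why the interval is fragile.** With treatment as the only covariate, median regression estimates the difference of the two sample medians. With n per arm, its large-sample standard error is √[1/(4n·f_L²) + 1/(4n·f_R²)], where f_L and f_R are the densities at each arm's median. For integer counts these densities do not exist. Software substitutes a smoothed value, and the interval width then reflects the smoothing.

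**4. Simulation.** Counts were drawn as zero with a set probability, otherwise from a negative-binomial hurdle model: 371 per arm, 300 trials per setting, kernel standard errors. All zero fractions and means are assumptions.

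| Zeros, liberal / restrictive | True median difference | True mean difference | Coverage of 95% quantile-regression CI |
|---|---|---|---|
| 5% / 65% | 3 | 2.55 | 85.3% |
| 5% / 50% | 3 | 2.23 | 39.7% |
| 5% / 45% | 2 | 2.12 | 85.0% |
| 40% / 40% | 0 | 0 | 100% |
| 55% / 80% | 0 | 0.95 | 95.7% |
| 20% / 65% | 1 | 0.90 | 99.7% |

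The large-sample unequal-variance CI for the mean difference covered 94.7% to 95.3% in all six settings.

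Two further sets of runs with 364 per arm agree:
- In one, with 5% liberal zeros, quantile-regression coverage was 48% at 50% restrictive zeros, 73% at 65% restrictive zeros with higher liberal use, and 97% to 100% in three other settings. The mean-difference CI covered 93% to 95%.
- In the other, with 45% to 65% restrictive zeros, quantile-regression coverage ran from 53% and 70% up to 100%. The mean-difference CI covered 94% to 96.5%.

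The 48% setting shows the mechanism. The estimate was 1 in 146 trials and 2 in 143 of 300, with a median CI width of 0.65. An interval of that width centred on 1 runs from 0.675 to 1.325 and cannot contain 2.

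A percentile bootstrap of the median difference is no remedy: in the six settings of the table its interval had zero width in 2% to 91% of trials.

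**5. One median difference, several mean differences.** Among settings with a true median difference of 2, the true mean difference ran from 1.29 to 2.24 units in one set of runs (ratio 2.24 / 1.29 = 1.7), from 1.21 to 2.27 in a second (1.9), and from 0.94 to 2.16 in a third (2.3). Over an arm of 371, the first range is (2.24 − 1.29) × 371 = 352 units of blood.

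**6. Student or Welch.** With n per arm, the pooled squared standard error is [(s₁² + s₂²)/2] × (2/n) = (s₁² + s₂²)/n, which equals Welch's. With 1:1 allocation the choice between them barely matters; the switch to a median does.

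**The case against.** The strongest reply is that the plan already does most of what is asked. The mean difference is first-line, overview Table 1 lists only the t-test, and the results shell shows means. The fallback is conditional, and without a normality criterion or a zero fraction its use cannot be called certain. This stands as a limit on the wording. It does not remove the problem, because counts of this shape will hardly be judged normal and the text then directs the analyst away from the mean.

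Second, quantile regression reaches this outcome only through a general line in the revision table. That is correct, and the point does not rest on any difference between that line and the current text. If the line does not apply, the bullet names no interval method at all, and a median difference of tied counts remains a coarse measure.

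Third, undercoverage is not universal. Several settings gave 95% or more. The lowest figures come from a knife edge, with half of the restrictive arm at zero, where the restrictive median is itself barely defined. This also stands: the fault is uncontrolled coverage, not failure everywhere.

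A reader might infer that the fallback would hide the difference in blood use. The documents do not support that. A median difference of zero despite a difference in means appeared only with 55% of liberal and 80% of restrictive patients at zero, which fits poorly with a liberal trigger equal to the entry haemoglobin. In the other settings with a treatment difference, the median difference was 1 to 3 units. The Wilcoxon test and the interquartile ranges would also show the separation.

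**Conclusion.** The point holds as a minor one. For RBC units per patient, the stated fallback replaces a well-behaved summary with one that moves in whole units, has an interval of uncontrolled coverage (about 40% to 100%, against about 93% to 96.5% for the mean difference), and can stand for roughly a twofold range of mean extra units.

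The size rests on assumed zero fractions and count distributions, and on reading the version 1.1 row as covering this bullet. The expectation of many restrictive-arm zeros is inferred from the triggers in section 3.1. The outcome is tertiary and exploratory, the Wilcoxon p-value does not depend on the interval method, and no primary or secondary analysis is touched.

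**What to change.** In section 6.2.3 and the matching cell of overview Table 1, state that RBC units per patient are compared by the mean difference with a Welch or bootstrap 95% CI whatever the distribution, as the Table 3 shell already shows. Give medians with interquartile ranges, and the proportion receiving at least 1 unit, as description. Drop the median-difference CI for this outcome and keep quantile regression for ventilation time and lengths of stay. If the Wilcoxon test is kept, it can stand beside the mean difference.

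The cost is one sentence and one table cell, with no new data. The small downside is that a mean is more sensitive to a few heavily transfused patients; the median and interquartile range reported alongside would show this.

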1.6 Abbreviations

- CI – Confidence interval
- CT – Computed Tomography
- DSMC – Data Safety and Monitoring Committee
- EQ-5D-5L – EuroQoL 5-Dimension 5-Level
- EQ-VAS – Visual Analogue Scale of the EuroQoL questionnaire
- FIM – Functional Independence Measure
- GCS – Glasgow Coma Score
- GOSe – Glasgow Outcome Scale extended
- Hb – Hemoglobin
- HR – Hazard ratio
- ICU – Intensive Care Unit
- MICE – Multivariate Imputation by Chained Equations
- OHRI – Ottawa Health Research Institute
- OR – Odds ratio
- PHQ-9 – Patient Health Questionnaire-9
- QOLIBRI – Quality of Life after Brain Injury
- RBC – Red Blood Cell
- RR – Risk ratio
- SAE – Serious Adverse Events
- SAP – Statistical Analysis Plan
- TBI – Traumatic Brain Injury
- tSAH – traumatic Subarachnoid Hemorrhage
- VAS – Visual Analogue Scale

Section 2: Introduction

2.1 Background and Rationale

Traumatic brain injury (TBI) is the leading cause of mortality and long-term disability in young adults¹. Despite the high prevalence of anemia and red blood cell transfusion in patients with TBI, the optimal hemoglobin (Hb) transfusion threshold is unknown². We undertook a randomized trial to evaluate whether a liberal transfusion strategy improves clinical outcomes compared with a restrictive strategy.

2.2 Objectives

Primary objective:

To evaluate the effect of liberal (experimental) against a restrictive (control) red blood cell (RBC) transfusion strategy using the Glasgow Outcome Scale extended (GOSe) to assess neurological outcome at 6 months. GOSe comprises eight ranking levels from 1 (death, least favourable outcome) to 8 (upper good recovery, most favourable outcome)³.

Secondary objectives:

To evaluate the effect of transfusion strategies on functional outcome, quality of life, depression and mortality.

Tertiary objectives:

To evaluate the effect of transfusion strategies on the incidence of transfusion-related complications, infections, Hb levels, number of RBC units transfused, and length of stay in the hospital and the intensive care unit (ICU).

Section 3: Study Methods

3.1 Trial Design

HEMOTION is a pragmatic, parallel group, multi-centre, open label blinded-endpoint, randomized trial⁴. Once reaching a Hb ≤ 100 g/L and after a site investigator has confirmed eligibility, participants will be randomly allocated to either a liberal (experimental) or a restrictive (control) RBC transfusion strategy. The trial intervention is initiated within 3 hours in patients meeting the threshold for transfusion in their respective group. All primary and secondary outcomes are assessed centrally by trained research personnel blinded to the intervention to minimize the risk of bias during data collection. Tertiary outcomes are assessed at participating sites, unblinded to the intervention but using standardized definitions.

The control strategy: Patients in the restrictive transfusion strategy group receive an RBC transfusion only if their Hb is ≤ 70 g/L.

The experimental strategy: Patients in the liberal transfusion strategy group receive an RBC transfusion if their Hb is ≤ 100 g/L. This threshold, shown to be effective in maintaining adequate cerebral oxygenation, is considered acceptable by clinicians caring for critically ill patients with neurological injuries.

3.2 Randomization

Patients are randomized by the research coordinator using a secure, web-based, central, concealed, computerized randomization portal to allocate patients in a 1:1 ratio to either a liberal (experimental) or a restrictive (control) RBC transfusion strategy. Randomization is done with variable permuted blocks of 4 and 6, stratified by site. Staff members of the Ottawa Methods Centre of the Ottawa Health Research Institute (OHRI) who are not involved in the trial implementation generated the randomization sequence. Analysis of the primary and secondary outcomes will be done by biostatisticians blinded to the intervention. They will also carry out analyses of tertiary outcomes that can be performed without unblinding (i.e., infections, length of stay). Analyses of other tertiary outcomes that require unblinding or will inevitably lead to unblinding (i.e., transfusion-related complications, Hb levels, number of RBC units transfused) will be done by independent biostatisticians not involved in the blinded analyses of other outcomes.

3.3 Sample Size

The sample size was calculated based on the proportion of patients who will experience an unfavourable outcome (i.e., GOSe ≤ 4 , which corresponds to upper severe disability). Assuming a 40% risk of unfavourable outcome in the control group^{5,6}, a sample size of 712 patients was originally estimated to detect an absolute risk reduction of 10% with a power of 80% and a type 1 error of 5%. This sample size calculation was conservative as it was based on the most widely-used definition of an unfavourable outcome in TBI using a simple dichotomous cut-off of the GOSe. Based on simulated data, the sliding dichotomy analysis is expected to increase the ability to observe the planned effect size with 95% power⁷. Initially, we had not adjusted the sample size for dropouts, given our experience with the prospective observational TBI-Prognosis study, where we did not encounter loss to follow-up when measuring a similar outcome using the same schedule.

3.4 Framework

We hypothesize that a liberal transfusion strategy, compared to a restrictive strategy, will improve 6-month neurological outcomes of critically ill patients admitted to the ICU following a moderate or severe TBI. We therefore use a superiority framework.

3.5 Statistical Interim analyses and stopping guidance (if applicable)

In 2022, a planned interim analysis of the primary outcome was conducted at 50% of enrollment. The data was tested using the Haybittle-Peto criterion ($p<0.001$). At this point, the Data Safety Monitoring Committee considered there was not enough evidence to stop the trial for efficacy (see [Appendix 1](#)). Considering the use of the Haybittle-Peto criterion, the final analysis of the primary outcome will be conducted at $p<0.05$. To account for an estimated 2% dropout rate (consent withdrawals and losses to follow-up) based on observed aggregate rates at the interim analysis, the final sample size was increased to 742, using the formula proposed by Lachin ($N = n/(1 - \%)^2$)⁸, where n is the original sample size, % is the proportion of dropouts, and N the new sample size).

3.6 Timing of final analysis

The trial is due to finish with the last 6-month follow-up assessment (scheduled in fall 2023, as the last patient was enrolled on April 13, 2023). The statistical analysis plan will be made public before the database is cleaned, verified, and definitively locked. Final analysis will be commenced once the final lock has been confirmed by the principal investigators.

3.7 Timing of outcome assessment

Primary outcome:

- GOSe [6 months]

Secondary outcomes:

- Mortality [In the ICU, in hospital and at 6 months]
- Functional Independence Measure (FIM) [6 months]
- EuroQoL 5-Dimension 5-Level (EQ-5D-5L) [6 months]
- Quality of Life after Brain Injury (QOLIBRI) [6 months]
- Patient Health Questionnaire-9 (PHQ-9) [6 months]

Tertiary outcomes:

- Red blood cell transfusion [In the ICU]
- Lowest Hb [In the ICU]
- Infections [In the ICU]
- Length of mechanical ventilation [In the ICU]
- Length of stay [In the ICU and in the hospital]
- Transfusion complications [In the ICU]

A +/- 2-week time window was allowed for the assessment of the primary and secondary outcomes.

[figure not shown]
Section 4: Statistical Principles

4.1 Confidence Intervals and P-values

The statistical uncertainty of all point estimates for the primary and secondary outcomes will be expressed as two-sided 95% confidence intervals (CI). The treatment effects for all outcomes will be tested at a 0.05 level of significance.

4.2 Adherence and protocol deviations

Potential protocol deviations and violations are reported to the Coordinating Centre within 72 hours and further classified into four categories (figure below), reflecting the following situations wherein: (1) an RBC transfusion occurred while the Hb threshold is not reached, (2) more than one unit is transfused without reassessing the Hb level between transfusions, (3) the delay between reaching the transfusion threshold and transfusion is greater than 3 hours or a transfusion never occurred despite reaching the transfusion threshold and (4) no transfusion occurred in the context of life-sustaining therapy withdrawal. Using a standard operating procedure detailed in the Study Protocol version 3.0, an adjudication committee will determine whether each reported event represents a protocol violation, a protocol deviation or neither.

4.3 Analysis populations

Intention-to-treat population. This population includes all randomized TBI patients except those who withdrew consent or were lost to follow-up. Baseline characteristics for the intention-to-treat population will be reported in the main manuscript.

Per-protocol population: This population includes all patients within the intention-to-treat group, except those who were allocated to the liberal strategy but were not transfused within a 24-hour time window after reaching Hb ≤ 100 g/L (protocol violation category #3), and those who were allocated to the restrictive strategy but were transfused despite not reaching their transfusion threshold of ≤ 70 g/L, or received more than one unit without reassessing the Hb despite the absence of ongoing important bleeding (protocol violation category #1 and 2). Baseline characteristics for the per-protocol population will be reported in an online Supplementary Appendix.

For the patients included and excluded from the per-protocol population, the median time to transfusion and the mean pretransfusion Hb level will be reported according to the treatment allocation.

Section 5 – Trial Population

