5.2 Withdrawal/Follow-up

The loss to follow-up rate is expected to be very low⁹. When a patient is lost to follow-up, the 6-month GOSe will be missing, therefore, this patient cannot be included in the analysis of the primary outcome. Whenever possible, such patients will be included in the secondary and tertiary outcome analyses.

No data will be analyzed for patients who withdraw consent, but such patients will be listed in the CONSORT diagram.

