6.2 Analysis Methods

All analyses will be performed using the intention to treat principle (see Section 4.3). The main analysis for the primary and secondary outcomes will be adjusted for sex. It will also be adjusted for site, as there are expected variations in TBI mortality between centers, which may be explained in part by regional variations in approaches to discontinuation of life-sustaining therapies²⁰. All treatment effects and differences between groups will be reported with their corresponding 95% CIs. Analyses are summarized in [Table 1](#) and will be reported as outlined in [Appendix 2](#).

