6.2.1 Primary outcome analysis

6.2.1.1 Main analysis of the primary outcome:

The null hypothesis states that the proportion of patients with an unfavourable outcome at 6 months, based on a sliding dichotomy of the GOSe score, are equal regardless of the RBC transfusion strategy.

For the main analysis, we will use the sliding dichotomy definition of the primary outcome described in section 6.1. The primary outcome will be analyzed using robust hierarchical Poisson regression, with study site modelled as a random intercept. Risk ratios and absolute risk reduction will be reported. We opted for robust Poisson regression²¹ rather than logistic regression to avoid reporting odds ratios, which systematically overestimate risk ratios and are frequently misinterpreted by clinicians^{22,23}. Our approach to handling missing covariates to determine sliding dichotomy thresholds is outlined in [section 6.3](#). The distribution of GOSe scores will also be presented graphically in the main manuscript (see Figure 1 in [Appendix 2](#)); distributions according to each predicted prognosis tertile will be presented in an online Supplementary Appendix.

6.2.1.2 Sensitivity analyses of the primary outcome:

We will evaluate the robustness of our findings for the main analysis of the primary outcome by conducting sensitivity analyses under various methodological assumptions:

- Multiple imputation. We will use Multiple Imputation by Chained Equations (MICE) for missing covariates, as outlined in [section 6.3](#).
- Complete case analysis. We will only include patients for whom no covariates to calculate the TBI-IMPACT prognostic score were imputed using conditional estimation (see [section 6.3](#)).
- Per protocol analysis. See [section 4.3](#).
- Best case-worst-case scenario. We will include randomized patients with missing primary outcome due to consent withdrawal or loss to follow-up; patients who were randomized by error will not be included in this analysis. In the best-case scenario, patients with missing primary outcomes will be considered as having a favourable outcome if randomized in the liberal strategy and as having an unfavourable outcome if randomized in the restrictive strategy. In the worst-case scenario, patients with missing primary outcomes will be considered as having an unfavourable outcome if randomized in the liberal strategy and as having a favourable outcome if randomized in the restrictive strategy.

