§ In this analysis we will include patients with missing primary outcome due to consent withdrawal or lost to follow-up; patients randomized by error will not be included. In the best-case scenario, patients with missing primary outcome will be considered as having a favourable outcome if randomized in the liberal strategy and as having an unfavourable outcome if randomized in the restrictive strategy. In the worst-case scenario, patients with missing primary outcome will be considered as having an unfavourable outcome if randomized in the liberal strategy and as having a favourable outcome if randomized in the restrictive strategy.

¶ Adjusted for sex and covariates included in the TBI-IMPACT Prognostic model, with a random intercept for site. Missing covariates will be addressed by multiple imputation using MICE.

** Includes only patients for whom sex and other covariates in the TBI-IMPACT Prognostic model were not missing

Appendix 1

April 08, 2022

[name]
Professor, Department of Anesthesiology and Critical Care Medicine
Université Laval, Québec, Québec, Canada

Object: HEMOTION Trial - Interim analysis

Dear [name],

The DSMC of the trial was presented the interim analysis report on April 04, 2022.

We have since reviewed the DSMC report including the study metrics and the interim analysis at 50% enrollment. Safety data and compliance data were reviewed as part of this report.

The DSMC recommends that the study continues enrollment without changes.

Sincerely,

[name] MD
Chair, HEMOTION DSMC

Appendix 2

Table 1. Characteristics of the Patients at Baseline.*

Characteristic	Liberal Strategy (N = xxx)	Restrictive Strategy (N = yyy)
Demographics		
Age — yr	99.9±99.9	99.9±99.9
Female sex — no. (%)	xxx (xx.x)	yyy (yy.y)
Race and ethnicity — no. (%)		
	Black or African-American	
	Asian	
	First Nations or Aboriginal	
	Hispanic or Latino	
	White	
	Other/unknown	
Positive qualitative drug screen — no./total no. (%)		
Positive blood ethanol level — no./total no. (%)		
Congestive heart failure — no. (%)		
Ischemic heart disease/myocardial infarction — no. (%)		
Previous traumatic brain injury, including concussion — no. (%)		
Chronic anemia — no. (%)		
Mechanism of injury		
Cause of injury — no. (%)		
	Motor vehicle accident	
	Pedal cycle, Motorcycle, scooter, or other all-terrain vehicles accident	
	Pedestrian injured in transport accident	
	Assault	
	Other	
Extracranial injury — no. (%)		
Injury Severity Score†		

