* The Glasgow Outcome Scale extended (GOSe), measured at 6-month, comprises eight ranking levels from 1 (death, least favourable outcome) to 8 (upper good recovery, most favourable outcome). The primary outcome was centrally assessed by blinded trained personnel.

† The treatment effect is a risk ratio unless otherwise indicated. Confidence intervals have not been adjusted for multiplicity, and inferences drawn from the intervals may not be reproducible.

‡ According to a sliding dichotomy of the GOSe. The sliding dichotomy approach is based on International Mission for Prognosis and Analysis of Clinical Trials in TBI (TBI-IMPACT) Core+CT+Lab prognostic model, which includes admission characteristics (age, motor score, pupils, hypoxemia, hypotension, CT classification, traumatic tSAH on CT, epidural mass on CT, glycemia and Hb). When necessary, we used conditional estimation for missing covariates to calculate an individual TBI-IMPACT score for each patient. Patients will be split into 3 tertiles based on their predicted risk of unfavourable outcome (mortality/vegetative state/severe disability) at 6 months. Patients categorized in the low-risk group will be considered to have an unfavourable outcome if the 6-month GOSe is ≤ 5 (i.e., death, vegetative state, lower and severe disability, or lower moderate disability). Patients in the intermediate risk group will be considered to have an unfavourable outcome if the 6-month GOSe is ≤ 4 (i.e., death, vegetative state, or lower and severe disability). Patients in the high-risk group will be considered to have an unfavourable outcome if the 6-month GOSe is ≤ 3 (i.e., death, vegetative state or lower severe disability). Analyses are adjusted for sex, with a random intercept for site.

§ The complete case analysis includes only patients for whom no covariate to calculate the TBI-IMPACT prognostic score was imputed using conditional estimation.

¶ The per protocol analysis excludes patients who were allocated to the liberal strategy but were not transfused within a 24-hour time window after reaching Hb ≤ 100 g/L, and those who were allocated to the restrictive strategy but were transfused despite not reaching the transfusion threshold of ≤ 70 g/L or received more than one unit without reassessing the Hb despite the absence of ongoing important bleeding.

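### The SAP gives contradictory rules on which analyses include patients lost to follow-up and patients who withdrew consent

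*SAP*

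**What the plan says.** **Lost patients.** Section 4.3 says of the intention-to-treat population: "This population includes all randomized TBI patients except those who withdrew consent or were lost to follow-up". Section 6.2 opens with "All analyses will be performed using the intention to treat principle (see Section 4.3"), so that set governs every outcome. Section 5.2 takes lost patients out of the primary outcome analysis only, and then adds: "Whenever possible, such patients will be included in the secondary and tertiary outcome analyses".

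**Withdrawn patients.** Section 5.2 states: "No data will be analyzed for patients who withdraw consent, but such patients will be listed in the CONSORT diagram". Section 6.2.1.2, describing the best-case/worst-case analysis, states: "We will include randomized patients with missing primary outcome due to consent withdrawal or loss to follow-up". Table 1 footnote § repeats this: "In this analysis we will include patients with missing primary outcome due to consent withdrawal or lost to follow-up". In the Appendix 2 shell for Table 2, footnote ‡ is attached to the sliding-dichotomy rows, including those under Sensitivity Analyses, and says: "Analyses are adjusted for sex, with a random intercept for site".

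**Related points.** Section 6.3 does not impute missing outcomes. Section 3.5 gives one pooled dropout figure: "To account for an estimated 2% dropout rate (consent withdrawals and losses to follow-up"). Withdrawals and losses are not reported separately.

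**The concern.** Each pair of rules gives different instructions for the same patients.

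A patient lost before 6 months may already have a known ICU and hospital survival status, infections, number of units transfused and length of stay. The planned frailty models can also use survival time up to the last contact. Sections 4.3 and 6.2, read as written, discard all of this; section 5.2 keeps it. Section 4.3 also ties the baseline table to its own set. If section 5.2 is followed for outcomes, the baseline table leaves out patients who are counted in the outcome table. The label is loose as well: a set that drops randomized patients because follow-up is missing is an available-outcome set, not intention-to-treat in the usual sense.

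For withdrawn patients, what is at stake is the membership of the best-case/worst-case analysis. Multiple imputation in this SAP covers covariates only, so this is the one planned analysis that tests what missing GOSe values could do to the primary result.

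**Working it through.** **1. Rules side by side**

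| Patients | Analysis | Rule A | Rule B |
|---|---|---|---|
| Lost | Primary outcome | 4.3: out | 5.2: out (agree) |
| Lost | Secondary, tertiary | 4.3 with 6.2: out | 5.2: in where possible |
| Withdrawn | Primary outcome | 4.3: out | 5.2: out (agree) |
| Withdrawn | Best/worst case | 5.2: no data analysed | 6.2.1.2 and Table 1 §: in |

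The main primary analysis is consistent. The second and fourth rows conflict.

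**2. The SAP's own sample size reproduces**

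For 40% versus 30%, 80% power and 5% two-sided error, the calculation gives 356 per arm, or 712. Inflation for dropout gives 712 / (1 − 0.02)² = 741.4, against the stated 742. The sample size is not in question.

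**3. Patients involved**

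0.02 × 742 = 14.84, about 15 patients, or 7.42 per arm if evenly split (assumed). Observed patients per arm: 371 − 7.42 = 363.58. The same 15 or so patients underlie both conflicts: the more of them withdrew, the fewer were lost.

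**4. Effect on the best-case/worst-case bounds**

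Assumed risks among observed patients are 30% (liberal) and 40% (restrictive). They come from the sample-size section, which uses the fixed GOSe ≤ 4 cut. The SAP gives no rate for the sliding dichotomy, so these are illustrative.

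Observed events: liberal 0.30 × 363.58 = 109.07; restrictive 0.40 × 363.58 = 145.43. Observed risk difference: −10.0 points.

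*All missing patients included, as in 6.2.1.2 (n = 371 per arm):*
- Best case: 109.07/371 − (145.43 + 7.42)/371 = 29.4% − 41.2% = −11.8 points; RR 0.71 (0.59 to 0.87).
- Worst case: (109.07 + 7.42)/371 − 145.43/371 = 31.4% − 39.2% = −7.8 points; RR 0.80 (0.66 to 0.98).

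*Withdrawals barred, as in 5.2, assuming they are half of the missing (3.71 lost per arm; n = 367.29):*
- Best case: 109.07/367.29 − 149.14/367.29 = −10.9 points.
- Worst case: 112.78/367.29 − 145.43/367.29 = −8.9 points; RR 0.78 (0.64 to 0.95).

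The best-to-worst range is therefore about 4.0 points under 6.2.1.2 and about 2.0 points under 5.2.

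**5. Dependence on the unknown share of withdrawals**

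| Withdrawals as share of missing | Change in worst-case bound (points) | Change in best-case bound (points) |
|---|---|---|
| 25% | 0.5 | 0.4 |
| 50% | 1.1 | 0.9 |
| 75% | 1.6 | 1.3 |
| 100% | 2.2 | 1.8 |

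Intervals are unadjusted Wald intervals on the log risk ratio; clustering by site is ignored.

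**6. Lost patients**

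The first conflict is not put into effect-size terms. The SAP gives neither the number lost nor the secondary event rates. At most about 15 patients (2%) could leave or enter a denominator.

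**The case against.** The strongest reply is that the specific rule prevails over the general one. Section 5.2 deals specifically with lost patients, so a sensible analyst would follow it and read section 6.2 as invoking a principle rather than fixing every denominator. The table shells fit that reading: they allow outcome-specific totals, and the FIM footnote counts missing data separately. For withdrawn patients, section 6.2.1.2 and Table 1 footnote § both name consent withdrawal as a reason for inclusion. The outcome is assigned by arm, so no GOSe is taken from the patient, and arm and site are already in the site-stratified randomization record. On this view a one-line clarification is enough.

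Part of this stands. The intended practice can be guessed, the effect is small, and the primary analysis is unaffected. But the SAP states no order of precedence, and section 6.2 points to 4.3, not to 5.2. The proposed reading must also let section 5.2 prevail for lost patients and be overridden for withdrawn ones. Nor is the assigned outcome the only item used: the analysis needs each patient's arm and, by footnote ‡, sex and site. Section 5.2 allows no exception for these.

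**Conclusion.** The point holds, with high confidence, and should be fixed. The SAP contains two contradictions: whether lost patients enter the secondary and tertiary analyses, and whether withdrawn patients enter the best-case/worst-case analysis. The main primary analysis is sound on this point, since sections 4.3 and 5.2 agree on its set.

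The consequence is modest: about 2% of patients, and a shift of at most 2.2 points in the worst-case bound and 1.8 points in the best-case bound. With half of the missing patients assumed withdrawn, the conclusion does not change. These figures rest on the pooled 2% dropout, an even split by arm, an assumed share of withdrawals, and risks borrowed from the fixed GOSe ≤ 4 calculation.

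**What to change.** 1. **Section 4.3.** Define intention-to-treat as all randomized patients by allocated arm. Name the primary analysis set separately, as intention-to-treat patients with an observed 6-month GOSe.
2. **Secondary and tertiary outcomes.** Analyse each in all intention-to-treat patients who have that outcome and whose data may be used, with survival censored at last contact.
3. **Sections 5.2 and 6.2.1.2.** Reconcile them in one of two ways:
   - state an exception that lets withdrawn patients enter the best-case/worst-case analysis with only the data that consent permits (for example arm and site), and say whether the sex adjustment is then dropped; or
   - restrict that analysis to lost patients, and change section 6.2.1.2 and Table 1 footnote § to match.
4. **Patients randomized by error (secondary).** Section 6.2.1.2 excludes them from the best-case/worst-case analysis and section 4.3 is silent. State one rule for the main and sensitivity sets.

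The cost is SAP wording only. Denominators will differ slightly between outcomes.
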